5.11 Interim and Final Analysis and Reporting

Interim and final reports [6] will be submitted to the Committee for Medicinal Products for Human Use (CHMP) in accordance with the vernakalant Periodic Safety Update Report (PSUR) schedule, beginning with the 18-month, 24-month reports and then annually thereafter until study completion. The interim and final analyses will address each of the study's primary and secondary objectives and will include descriptive summaries of:

- Patient disposition and enrolment
- Patient characteristics (medical history, presenting conditions, and AF disease history)
- Hospital characteristics and medical encounter
- Details of vernakalant IV administration, dosing, and monitoring
- Administration of concomitant treatment modalities
- Frequencies and incidences of HOIs and SAEs following administration. Two-sided 95% confidence intervals around rates of HOIs will be computed. Line listings of all HOIs and SAEs as well as narratives will be required for interim reports.
- Effectiveness (rate of successful cardioversion)
- Country-specific tables, as described in Section 4.3 Subgroup Analysis, will be included in the Appendix of the interim and final reports.

All interim reports will clearly indicate the total number of patients included, and any additional information included in the data extraction used for the report.

In addition, the final study report will summarise the frequency of non-serious AEs. A table of NSAEs will display numbers and the cumulative incidence of all AEs and will be included for the final report (**Table 17**). The final study report is expected to be prepared after the registry is completed (currently planned for 2016). The timing of the interim and final analysis may be adjusted based on actual site recruitment and data accrual rates.

Full explanation of study methods, status of study site and patient enrolment, results, and discussion and interpretation will be included with interim and final study reports.

In addition, the following reporting conventions will be applied: All percentages will be carried out to one decimal place. Mean, median, Q1, Q3, minimum, and maximum will be carried out one decimal place further than the manner in which the data is reported. The standard deviation will be carried out 2 decimal places farther than the manner in which the data is reported. Standard rounding rules at the last decimal place apply. When appropriate, additional information will be provided in the specifications.

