**Vernakalant IV Sterile Concentrate Prospective Safety Registry Study**

Sponsor Protocol Identifier: 6621-049-00

3 August 2016

Dosing/Administration of Vernakalant IV (total number of infusions, total dose with each infusion, start/stop time for each infusion, amount of time between each infusion, time to successful conversion, and methods of site monitoring of patients during and following vernakalant infusion per SmPC guidance)	Medical record	X	X
Administration of therapies for restoration/maintenance of sinus rhythm during the index hospitalisation* (IV and oral rhythm control pharmacologic agents, electrical cardioversion, Maze ablation, pacemaker or ICD implantation or any other surgical procedure to restore sinus rhythm, start/stop time for IV or electrical treatments)	Medical record	X	X*
Mandatory reporting of pre-specified medically significant HOIs (see section 8 for definitions and reporting requirements)	Investigator/Site staff	X	X
Mandatory reporting of SAEs (see section 8 for definitions and reporting requirements)	Investigator/Site staff	X	X

\*Data on concomitant medications and therapies (oral, IV meds, electrical cardioversion, and/or surgical procedures) for restoration/maintenance of sinus rhythm during the index hospitalization for stays exceeding 24 hours following last infusion of vernakalant IV will be recorded up to 7 days following the last vernakalant IV infusion.

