### **8.4 Reporting by Investigators**

Reporting of all SAEs and HOIs that occur during the study follow-up period (earlier of 24 hours post vernakalant IV administration or hospital discharge) are mandated as part of this protocol and should be reported to the study CRO by the study investigator within 24 hours of identification. All serious AEs and HOIs that occur during the study follow-up period will be recorded by the investigator in the serious AE eCRF and will result in an automated notification to the study's CRO.

All subjects/patients with SAEs must be followed up for outcome of the event. Any follow-up information on the SAE should be provided by the investigator to the CRO within the same reporting period (within 24 hours of identification).

An investigator who is a qualified physician, will evaluate AEs for relationship to vernakalant IV according to the following categorisation:

- Definitely related
- Probably related
- Possibly related
- Probably not related
- Definitely not related

If a non-Cardiome Product is considered by the investigator to be co-suspect, the investigator is responsible for reporting the SAE to the manufacturer of the non-Cardiome Product.

If an investigator reports a non-serious AE, it will be collected in the non-serious AE eCRF.

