## Vernakalant IV Sterile Concentrate Prospective Safety Registry Study

Sponsor Protocol Identifier: 6621-049-00

3 August 2016

Reports of non-serious adverse reactions received by the CRO will be included in the end of study summary report to the CHMP.

The study investigator must comply with any applicable site-specific requirements related to the reporting of SAEs involving his/her patients to the Ethics Committee (EC that approved the study). When direct reporting by an investigator is not clearly defined by national or site-specific regulations, the study physician will be responsible for promptly notifying the concerned EC of any safety reports provided by the Sponsor and of filing copies of all related correspondence in the Site File.

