#### Non-serious AEs

Tables with counts of non-serious AEs will be provided and summarised by MedDRA SOC, HLT, and PT and stratified by relationship to the study drug once for the final study report. These summaries will be reported overall and stratified by method of patient enrollment.

**Secondary Objective 2:** *Characterise patients administered vernakalant IV in terms of patient demographics, medical history, and presenting conditions. Specific conditions to be summarised include:*

- *Heart failure, NYHA class*
- *Prolonged QT, severe bradycardia, sinus node dysfunction, second or third degree heart block, clinically meaningful valvular stenosis, hypertrophic obstructive cardiomyopathy, restrictive cardiomyopathy, constrictive pericarditis*
- *History of hyperthyroidism*
- *Severe aortic stenosis, low systolic BP*

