| | Time Since First Vernakalant Infusion | | | | | | | |
|-------------|--|-------------|---|-------------|--|----------|---|-------------|
| | 0 - < 2 hours from start of first infusion (N=xxx) ¹ | | 2- < 4 hours from start of first infusion (N=xxx) ¹ | | 4- 24 hours from start of first infusion (N=xxx) ¹ | | Overall (N=xxx) | |
| | Patients n (Cumulative Incidence ¹) | Events n | Patients n (Cumulative Incidence ¹) | Events n | Patients n (Cumulative Incidence ¹) | Events n | Patients n (Cumulative Incidence ¹) | Events n |
| Any NSAE | xx (x.x%) | xx | xx (x.x%) | xx | xx (x.x%) | xx | xx (x.x%) | xx |
| SOC 1 | xx (x.x%) | xx | xx (x.x%) | xx | xx (x.x%) | xx | xx (x.x%) | xx |
| HLT 1 | xx (x.x%) | xx | xx (x.x%) | xx | xx (x.x%) | xx | xx (x.x%) | xx |
| PT 1 | xx (x.x%) | xx | xx (x.x%) | xx | xx (x.x%) | xx | xx (x.x%) | xx |
| PT 2 | xx (x.x%) | xx | xx (x.x%) | xx | xx (x.x%) | xx | xx (x.x%) | xx |
| SOC 2 | xx (x.x%) | xx | xx (x.x%) | xx | xx (x.x%) | xx | xx (x.x%) | xx |
| HLT 2 | xx (x.x%) | xx | xx (x.x%) | xx | xx (x.x%) | xx | xx (x.x%) | xx |
| PT 1 | xx (x.x%) | xx | xx (x.x%) | xx | xx (x.x%) | xx | xx (x.x%) | xx |
| PT 2 | xx (x.x%) | xx | xx (x.x%) | xx | xx (x.x%) | xx | xx (x.x%) | xx |

¹Cumulative incidence calculated as the number of patients who have a specific pre-specified event starting during the study period, divide by the total number of patients enrolled, multiplied by 100.

Template of Table 17.1 will be applied to the following two tables. Please make sure in the header “Analysis Set” is changed to “Prospective Patients” and “Retrospective Patients”, respectively.

[figure not shown]
Table 17.2 Non-Serious Adverse Events by System Organ Class (SOC) and Preferred Term (PT) (Final Report) – Prospective Patients

Table 17.3 Non-Serious Adverse Events by System Organ Class (SOC) and Preferred Term (PT) (Final Report) – Retrospective Patients

Table 18 Number of Patients with Missing Information for Selected Critical Fields

| Critical Field | Prospective Patients (N=xxx) | Retrospective Patients (N=xxx) | Analysis Set (N=xxx) |
|---|------------------------------|--------------------------------|----------------------|
| Height | xx (xx.x%) | xx (xx.x%) | xx (xx.x%) |
| NYHA Heart Failure Class | xx (xx.x%) | xx (xx.x%) | xx (xx.x%) |
| Smoking Status | xx (xx.x%) | xx (xx.x%) | xx (xx.x%) |
| Stop Time (for each infusion) | xx (xx.x%) | xx (xx.x%) | xx (xx.x%) |

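### SAP Table 17 labels non-mandated reports of non-serious AEs as cumulative incidence, with no caveat, and drops the protocol's breakdown by relationship to study drug

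*SAP*

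**What the plan says.** **Reporting duty.** Under protocol 8.4, reports of SAEs and HOIs arising in the follow-up period "are mandated as part of this protocol and should be reported to the study CRO by the study investigator within 24 hours of identification". For other events the same section says only: "If an investigator reports a non-serious AE, it will be collected in the non-serious AE eCRF". The schedule of assessments (protocol 7.1.2) has a row for "Mandatory reporting of SAEs" and one for HOIs, and none for non-serious AEs. Protocol 8.6 adds: "Reports of non-serious adverse reactions received by the CRO will be included in the end of study summary report to the CHMP".

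**Protocol analysis.** Protocol 10.3 states: "Tables with counts of non-serious AEs will be provided and summarised by MedDRA SOC, HLT, and PT". These tables are to be "stratified by relationship to the study drug once for the final study report", and shown overall and by method of enrolment. Protocol 10.9 promises frequencies and cumulative incidence for HOIs and SAEs, but only frequencies for non-serious AEs.

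**SAP analysis.** SAP 5.11 states: "A table of NSAEs will display numbers and the cumulative incidence of all AEs". The Table 17.1 shell has four columns: 0 to <2 h, 2 to <4 h, 4 to 24 h, and overall. Each gives patients with a percentage headed cumulative incidence, and events. Its footnote takes the patients with a pre-specified event and says to "divide by the total number of patients enrolled, multiplied by 100". Tables 17.2 and 17.3 repeat the shell for prospective and retrospective patients. No column or row shows relationship to study drug; that appears for each event in Listing 3.

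**The concern.** Cumulative incidence requires that events be sought, or at least required to be reported, in everyone in the denominator. Here the denominator is every enrolled patient, but nothing obliges a site to record a non-serious AE. A patient whose site reported nothing counts as event-free.

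The report goes to the CHMP. Protocol section 3 prints pooled-trial adverse reaction percentages for a window ending 2 hours after infusion, and Table 17 has a 0 to <2 h column under an incidence label. A reader could set the two side by side and take a difference in capture for a difference in risk. Capture may also differ between prospectively enrolled patients and abstracted charts, which would affect a comparison of Table 17.2 with Table 17.3.

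Separately, the final report would lack a tabulation that the protocol promises.

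**Working it through.** Neither document gives an expected non-serious AE rate, a reporting completeness or a precision statement for Table 17, so there is no plan figure to reproduce.

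**Step 1. Is capture required anywhere?** Protocol 8.4 and 7.1.2 make reporting mandatory for SAEs and HOIs only. The key data elements in protocol 7.1.1, against which retrospective charts are abstracted (7.2.1), list the HOIs but no non-serious AEs. The assurance in protocol 7.2 that retrospective inclusion would not bias event rates downward is argued for HOIs and other rare events. SAP Table 18, on missing critical fields, has no line for AE capture.

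**Step 2. Does the label fit?** The Table 17 footnote uses essentially the wording that defines HOI incidence in the Table 8 series, including the reference to a pre-specified event. HOIs are pre-specified and their reporting is mandated. No non-serious AE is pre-specified, and reporting is not mandated. No caveat appears in SAP 5.11 or the Table 17 notes.

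**Step 3. Direction and possible size.** Let *c* be the share of patients with a given non-serious event for whom it is reported. With all enrolled patients in the denominator, and assuming entered reports are genuine:

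printed percentage = true incidence × *c*

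This is at or below the true incidence for any *c* up to 1. The documents do not give *c*; the range 10% to 100% is an assumption.

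For an illustrative true rate, take the vernakalant column in protocol section 3 and subtract the clinically meaningful events, because SAEs and HOIs are captured elsewhere:

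- hypotension: 7.6 − 1.2 = 6.4%
- atrial flutter: 10.0 − 0.1 = 9.9%
- bradycardia: 5.4 − 1.3 = 4.1%

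| *c* (assumed) | Hypotension | Atrial flutter | Bradycardia |
|---|---|---|---|
| 100% | 6.4% | 9.9% | 4.1% |
| 90% | 5.8% | 8.9% | 3.7% |
| 75% | 4.8% | 7.4% | 3.1% |
| 50% | 3.2% | 5.0% | 2.1% |
| 25% | 1.6% | 2.5% | 1.0% |
| 10% | 0.6% | 1.0% | 0.4% |

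For scale, 6.4% of the target 2,000 patients is 128. At *c* = 50%, 64 would be reported, and 64/2,000 = 3.2%.

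The remainder is only a proxy. The trials' clinically meaningful category includes events that led to discontinuation as well as SAEs, the trial population and ascertainment differ, and the trial window is not the same as any Table 17 column.

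**Step 4. Relationship.** Protocol 10.3 requires the non-serious AE tables to be stratified by relationship. Table 17 stratifies by time window instead. The data exist, since Listing 3 carries the five-level relationship.

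**The case against.** Most of the opposing case concerns how far the point can be pushed, and much of it stands.

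- **Size.** A reader might infer that Table 17 will show rates far below the true ones. The documents do not support that. They give no reporting fraction, and in a short in-hospital window capture could be nearly complete. Using only low completeness values would assume the conclusion. Using the all-event trial rates (7.6%, 10.0%, 5.4%) as the true rates would be wrong too, since they include serious events that belong in other tables.
- **Motive.** A reader might also infer that the protocol planned counts because it knew reporting would be incomplete. That cannot be shown. Protocol 10.3 also plans counts for SAEs, whose reporting is mandatory, and SAP 5.7 turns those into counts and cumulative incidence. The contrast in protocol 10.9 between incidence for HOIs and SAEs and frequencies for non-serious AEs is suggestive, no more.
- **Mitigation.** Tables 17.2 and 17.3 separate the enrolment methods, and Listing 3 preserves relationship. This helps in part. The split does not reveal completeness in either group, and a listing is not the stratified table the protocol requires. The final report will contain discussion and interpretation, where the limitation could be stated, but the SAP does not commit to stating it.
- **Weight.** Non-serious AEs serve no stated objective, and Table 17 is descriptive, without confidence intervals. This stands and limits the importance of the point.
- **Remedy.** Deleting the percentages would achieve little while N stays in the header, because readers can divide. This also stands, so relabelling is enough.

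**Conclusion.** The point holds as a mislabelled estimate plus a dropped tabulation. Followed as written, the SAP would present reports that nobody was required to make, divided by all enrolled patients, as cumulative incidence without a caveat. The figures are lower bounds that may understate true incidence by an unknown amount. The direction follows from the reporting rules, assuming entered reports are genuine. The size cannot be derived from the documents, and the illustrative range includes no understatement at all.

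The missing stratification by relationship is a plain departure from protocol 10.3 and needs no assumption. HOI and SAE results, whose reporting is mandated, are not affected. The change should be made because the table goes into a regulator-facing safety report and correcting it is nearly free.

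**What to change.** In SAP 5.11 and Tables 17.1 to 17.3:

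1. Present numbers of patients and numbers of events. Label any percentage *reported frequency*, not cumulative incidence.
2. Rewrite the footnote to remove the reference to a pre-specified event. State that reporting of non-serious AEs was not mandated, so incidence cannot be derived from the table.
3. Add the stratification by relationship to study drug required by protocol 10.3. The time-window columns may stay alongside it.

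The cost is SAP wording and table shells. No new data are needed, because relationship is already available for Listing 3.

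### SAP Table 17 labels non-serious AEs, whose reporting is not mandated, as cumulative incidence over all enrolled patients; each figure is only a lower bound

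*SAP*

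**What the plan says.** **Reporting duty.** Protocol 8.4 names the events that sites must send in: "Reporting of all SAEs and HOIs that occur during the study follow-up period" "are mandated as part of this protocol and should be reported to the study CRO". Non-serious AEs get a conditional sentence instead: "If an investigator reports a non-serious AE, it will be collected in the non-serious AE eCRF". The schedule of assessments in Protocol 7.1.2 has one mandatory row for HOIs and one for SAEs ("Mandatory reporting of SAEs"). It has none for non-serious AEs, and the key data elements in 7.1.1 do not list them.

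**Planned analysis in the protocol.** Section 10.3 states "Tables with counts of non-serious AEs will be provided and summarised by MedDRA SOC, HLT, and PT". Section 10.9 plans cumulative incidence for HOIs and SAEs in the final report, and frequencies for non-serious AEs.

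**Planned analysis in the SAP.** Section 5.11 first speaks of the frequency of non-serious AEs, then adds: "A table of NSAEs will display numbers and the cumulative incidence of all AEs". The Table 17.1 template prints this for 0 to <2, 2 to <4 and 4 to 24 hours and overall, by system organ class, high level term and preferred term. Footnote 1 gives the denominator: "divide by the total number of patients enrolled, multiplied by 100". Tables 17.2 and 17.3 repeat the template for prospective and retrospective patients.

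**The concern.** A cumulative incidence is the proportion of people followed who had the event. It needs ascertainment in everyone in the denominator. Table 17 puts every enrolled patient in the denominator but has no rule that ascertains non-serious AEs in every patient. Someone whose event was not reported cannot be told apart from someone who had none.

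At stake is what the final safety report can claim. A percentage headed cumulative incidence will be read as an estimate of risk, and nothing in the template warns against that. The split by enrolment method adds a second problem: bedside and chart-based collection may capture minor events differently, so a difference between Tables 17.2 and 17.3 may show reporting habits.

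**Working it through.** The documents give no non-serious AE rate, so there is no stated figure to reproduce. The check is on the definition.

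**1. Inputs**
- Numerator: patients with an investigator-reported non-serious AE (Protocol 8.4).
- Denominator: all patients enrolled (SAP Table 17.1, footnote 1).
- Imputation for unreported events: none (SAP 4.4).
- Share *s* of affected patients who have a report: not given. Assumed range 0.25 to 1.0.

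**2. Formula.** Let N be the denominator, A the patients who had the event and R those among them with a report. Assume that reported events are real.
- Quantity named in the table: A / N.
- Quantity printed: R / N = (s × A) / N = s × (A / N).
- R cannot exceed A, so the printed figure cannot exceed the incidence. They are equal only if every affected patient has a report (s = 1).
- Relative shortfall: 1 − s.

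**3. Assumed shares**

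| Assumed s | Printed figure as share of true incidence | Relative shortfall |
|---|---|---|
| 1.0 | 100% | 0% |
| 0.9 | 90% | 10% |
| 0.75 | 75% | 25% |
| 0.5 | 50% | 50% |
| 0.25 | 25% | 75% |

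The share may also vary between event terms and time windows, so one correction factor would not repair the table.

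**4. Prospective against retrospective.** Ratio of printed figures = (s_pro / s_retro) × true ratio. With equal true incidence and each share between 0.25 and 1.0, the printed ratio could lie anywhere from 0.25 / 1.0 = 0.25 to 1.0 / 0.25 = 4. The documents do not say whether the shares differ.

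**5. Safeguards elsewhere**
- Source verification in Protocol 8.5 covers SAEs and HOIs.
- Protocol 7.2's assurance that rates are not biased downward concerns HOIs and other rare events.
- SAP Table 18, on missing critical fields, has no non-serious AE row.
- No Table 17 footnote says that reporting was not mandated.

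**6. Denominator wording.** Footnote 1 divides by patients enrolled, whereas the analysis set in SAP 4.2 requires that vernakalant was given. Counting enrolled but untreated patients would lower the figures further, by an amount that cannot be derived here. The footnote also refers to a pre-specified event, as the HOI tables do; non-serious AEs are not pre-specified.

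**The case against.** The best defence is that nothing shows that any event was missed. A dedicated eCRF exists for non-serious AEs, investigators grade AEs in general for relatedness, and no sentence tells sites that they may leave non-serious events out. The table is descriptive, serves no numbered objective and appears once, in a final report that must explain its methods. N stays in the column header, so deleting the percentages would not stop anyone from computing them.

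Much of this stands, and it rules out three stronger readings that a reader might infer.

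- *Every rate is biased low.* This would need evidence of under-reporting. The documents show only that reporting is not mandated and that its completeness is unknown, which supports a lower bound and no more.
- *The size can be read from the trial rates in Protocol section 3.* Subtracting the clinically meaningful rate from the overall rate for hypotension gives 7.6% − 1.2% = 6.4%, which looks like a benchmark. The subtracted events include those that led to discontinuation, some of which may be non-serious. The trial window runs to 2 hours after infusion, whereas Table 17 counts from the start of the first infusion. Table 17 plans no confidence intervals, and neither document plans a comparison of it with trial rates.
- *The protocol chose counts because reporting is not mandated.* Protocol 10.3 also says counts for the SAE tables, where reporting is mandatory. Section 10.9 does keep cumulative incidence for HOIs and SAEs, but gives no reason.

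None of this rescues the label. A proportion of patients with a report is not an incidence when reporting is conditional.

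**Conclusion.** The concern holds in limited form. As written, SAP 5.11 and Tables 17.1 to 17.3 give the name cumulative incidence to a quantity that the data collection rules support only as a minimum. That conclusion rests on the limited reporting mandate, the conditional sentence on non-serious AEs and the all-enrolled denominator, and on the assumption that reported events are real.

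The shortfall is unknown and may be zero. The 25% to 100% range is an assumption that shows how the figure scales with completeness. A difference in completeness between prospective and retrospective patients is possible but not documented.

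Severity is low. The HOI and SAE analyses have mandated reporting and are not touched.

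**What to change.** In SAP 5.11 and Tables 17.1 to 17.3:

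1. Replace the cumulative incidence heading with counts of patients and events, or keep a percentage under the heading *proportion of treated patients with an investigator-reported non-serious AE (minimum)*. Either is acceptable; since N remains visible, the label matters more than whether a percentage is printed.
2. If a percentage is kept, use treated patients as the denominator, in line with the analysis set in SAP 4.2.
3. Replace footnote 1 with a statement that reporting of non-serious AEs was not mandated, that the figures do not estimate incidence, and that the prospective and retrospective tables should not be compared as rates.

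Protocol 10.3 also asks for these tables by relationship to study drug, whereas Table 17.1 is laid out by time window. The same edit can reconcile the two.

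The cost is SAP wording and one table template, with no new data. The downside is that the final report gives no incidence estimate for non-serious AEs, which the reporting rules could not support anyway.
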